4.3.2 Treatment discontinuation: Ipilimumab and/or nivolumab

Should the treating physician decide to discontinue treatment given suspicion for a drug-related side effect, the side effect should be attributed to one study drug to the best of the physician's ability. Either ipilimumab or nivolumab should be discontinued based on this attribution, or both if a definite attribution is not possible.

Ipilimumab and/or nivolumab should be discontinued permanently for the following:

- Any Grade 2 drug-related uveitis, eye pain, or blurred vision that does not respond to topical therapy and does not improve to Grade 1 severity within the re-treatment period OR requires systemic treatment
- Any Grade 3 non-skin, drug-related adverse event lasting > 7 days, with the following exceptions for laboratory abnormalities, drug-related uveitis, pneumonitis, bronchospasm, hypersensitivity reactions, infusion reactions, and endocrinopathies:
 - Grade 3 drug-related uveitis, pneumonitis, bronchospasm, hypersensitivity reaction, or infusion reaction **of any duration** (can be < 7 days) requires discontinuation
 - Grade 3 drug endocrinopathies adequately controlled with only physiologic hormone replacement do not require discontinuation
 - Grade 3 drug-related laboratory abnormalities do not require treatment discontinuation except:
 - Grade 3 drug-related thrombocytopenia > 7 days or associated with bleeding (aside from minor bleeds \leq Grade 1) requires discontinuation

NU Study Number: NU 16N03
BMS Study Number: CA 209-802

- Any drug-related liver function test (LFT) abnormality that meets the following criteria require discontinuation:
 - AST or ALT > 5-10 x ULN for > 2 weeks
 - AST or ALT > 10 xUL
 - Total bilirubin > 5 x ULN
 - Concurrent AST or ALT > 3 xULN and total bilirubin > 2 x ULN
- Any Grade 4 drug-related adverse event or laboratory abnormality, except for the following events which do not require discontinuation:
 - Grade 4 neutropenia < 7 days
 - Grade 4 lymphopenia or leukopenia
 - Isolated Grade 4 amylase or lipase abnormalities that are not associated with symptoms or clinical manifestations of pancreatitis. PI and Data Safety and Monitoring Committee (DSMC) should be consulted for Grade 4 amylase or lipase abnormalities.
 - Isolated Grade 4 electrolyte imbalances/abnormalities that are not associated with clinical sequelae and are corrected with supplementation/appropriate management within 72 hours of their onset

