4.8 Duration of Follow Up

All patients will be followed for adverse events for 30 days after last dose of nivolumab and or ipilimumab (100 days for SAEs), or until the patient starts a new treatment, whichever occurs first. Patients who discontinue treatment for unacceptable adverse event(s) will be followed until resolution or stabilization of the adverse event (i.e. the grade is not changing). If a patient stops treatment due to unacceptable adverse event(s) but has not demonstrated disease progression, then the patient will be followed with imaging studies every 12 weeks until the time of progression radiographically according to RECIST 1.1 criteria. In the event that a radiographic response is detected, then this event will be included as a response in the final analysis, and the time of progression used in calculation of the survival analysis. Patients will be seen in clinic every 4 weeks for the first 12 weeks after treatment discontinuation. Thereafter, patients will be followed for survival (by clinic visit or phone call) every 12 weeks for 2 years from treatment discontinuation or until death, whichever occurs first.

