¹⁴ Archival tissue will be collected at baseline for all patients (if available). Additional tissue may be collected (if feasible) during biopsies performed as standard of care during study participation. Please see separate lab manual for details.

¹⁵ Treatment will start within 7 days after registration, and continue until confirmed disease progression, unacceptable toxicity, or withdrawal of consent. See section **4.4** for conditions to continue treatment beyond initial progression.

¹⁶ Study procedures may take place within 24 hours prior to study treatment.

¹⁷ End of Treatment visit will occur 30 days (\pm 7 days) after stopping nivolumab or combination treatment, or before the patient starts new treatment, whichever occurs first. Adverse events will be recorded for up to 30 days after stopping treatment (SAE's for 100 days).

¹⁸ Patients will be followed every 4 weeks (\pm 7 days) by routine clinic visit for the first 12 weeks after treatment. Thereafter, patients will be followed (either by routine clinic visit or by phone) every 3 months for up to 2 years to document survival and disease progression. SAE's will be recorded for the first 100 days after treatment discontinuation.

¹⁹ Echocardiogram and/or ECG should be performed at screening as clinically indicated for patients with a history of congestive heart failure or at risk because of underlying cardiovascular disease or exposure to cardiotoxic drugs. Cardiac toxicities should be closely monitored throughout treatment.

²⁰ Tissue will be collected for Next Generation Sequencing any time prior to study treatment (we will accept archival tissue from the lesion demonstrating progression of recurrent/metastatic disease, as long as the patient has not received other treatment since that biopsy). Tissue will also be collected with any SOC biopsies throughout study treatment. If a patient has not had NGS performed from the lesion demonstrating PD, and the lesion is amenable to biopsy, the patient may agree to provide a fresh biopsy for standard-of-care NGS. If a biopsy is not feasible, is a high-risk procedure for patient, or the patient is not willing, he or she will be required to provide blood for ct DNA and will not be excluded from the study.

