7.3 Reporting of pregnancy and lactation

Although pregnancy and lactation are not considered adverse events, it is the responsibility of investigators or their designees to report any pregnancy or lactation in a subject (spontaneously reported to them), including the pregnancy of a male subject's female partner, that occurs during the trial or within 5 months after the last dose of study drug for FOCBP or 7 months for males with FOCBP partners. All subjects and female partners of male subjects who become pregnant must be followed to the completion/termination of the pregnancy. Pregnancy outcomes of spontaneous abortion, missed abortion, benign hydatidiform mole, blighted ovum, fetal death, intrauterine death, miscarriage and stillbirth must be reported as serious events (Important Medical Events). If the pregnancy continues to term, the outcome (health of infant) must also be reported.

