8.1.11 Safety and monitoring plan

All participants will be carefully followed for safety. Participants are seen by their study doctor and research nurse before each dose of nivolumab every 2 or 4 weeks. Safety evaluations at this time include a physical exam, vital signs, performance status assessment, and safety laboratory tests. The study team will continuously monitor participants for treatment side effects. Participants are instructed to inform their study doctor right away if they notice or feel anything different so the study doctor can check for side effects. The study doctor may be able to provide treatment for side effects. The study doctor may temporarily hold the study drug to reduce side effects. The study doctor will permanently stop the study drug if side effects are too severe and/or long lasting. All participants will be followed for side effects for 30 days from their last dose of nivolumab. Participants with ongoing side effects will continue to be followed until resolution or stabilization of the side effects. Because it is not known if nivolumab will be effective against this type of cancer, enrollment will stop after 12 participants are treated with nivolumab if none of them have their tumors shrink..

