Appendix C – Contraception Requirements

Investigators shall counsel FOCBP and male subjects who are sexually active with FOCBP on the importance of pregnancy prevention and the implications of an unexpected pregnancy. Investigators shall advise FOCBP and male subjects who are sexually active with FOCBP on the use of highly effective methods of contraception from the time of treatment initiation to 5 months (for FOCBP) or 7 months (for males with FOCBP partners) after the last dose of nivolumab. Highly effective methods of contraception have a failure rate of < 1% per year when used consistently and correctly.

At a minimum, subjects must agree to the use of two methods of contraception, with one method being highly effective and the other method being either highly effective or less effective as listed below:

HIGHLY EFFECTIVE METHODS OF CONTRACEPTION

- a) Male condoms with spermicide
- b) Hormonal methods of contraception including combined oral contraceptive pills, vaginal ring, injectables, implants, and intrauterine devices (IUDs) such as Mirena® by FOCBP subject or male subject's FOCBP partner. Female partners of male subjects participating in the study may use hormone based contraceptives as one of the acceptable methods of contraception since they will not be receiving study drug.
- c) Nonhormonal IUDs, such as ParaGard®
- d) Tubal ligation
- e) Vasectomy.
- f) Complete Abstinence*

*Complete abstinence is defined as complete avoidance of heterosexual intercourse and is an acceptable form of contraception for all study drugs. Subjects who choose complete abstinence are not required to use a second method of contraception, but female subjects must continue to have pregnancy tests. Acceptable alternate methods of highly effective contraception must be discussed in the event that the subject chooses to forego complete abstinence.

LESS EFFECTIVE METHODS OF CONTRACEPTION

- a) Diaphragm with spermicide
- b) Cervical cap with spermicide
- c) Vaginal sponge
- d) Male Condom without spermicide*
- e) Progestin only pills by FOCBP subject or male subject's FOCBP partner
- f) Female Condom*

[figure not shown]
*A male and female condom must not be used together

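### The contraception window in Appendix C and the End of Treatment visit do not fit a patient who stops nivolumab and continues ipilimumab alone

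*Combined protocol and SAP*

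**What the plan says.** Section 4.3.2 asks the physician to attribute a suspected drug-related side effect to one drug, and continues: "Either ipilimumab or nivolumab should be discontinued based on this attribution, or both if a definite attribution is not possible". Section 4.2.2 gives ipilimumab every 6 weeks until progression or unacceptable toxicity, with no maximum number of doses.

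The rules for the end of treatment use different reference dates:

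- **End of Treatment visit (5.0, footnote 17):** 30 days (±7) "after stopping nivolumab or combination treatment, or before the patient starts new treatment", whichever is first. Footnote 13 ties a correlative blood sample to this visit.
- **Contraception (Appendix C):** from the start of treatment to 5 months for females of childbearing potential (FOCBP), "or 7 months (for males with FOCBP partners) after the last dose of nivolumab".
- **Contraception (inclusion criterion 3.1.10):** throughout treatment and for a designated post-treatment period, with a reference to Appendix C for methods.
- **Pregnancy reporting (7.3):** pregnancies during the trial or "within 5 months after the last dose of study drug for FOCBP", and 7 months for males with FOCBP partners.
- **Side-effect follow-up:** 8.1.11 says "All participants will be followed for side effects for 30 days from their last dose of nivolumab"; 8.2.11 has the matching sentence for ipilimumab; 4.8 says "All patients will be followed for adverse events for 30 days after last dose of nivolumab and or ipilimumab".

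**The concern.** Footnote 17 and Appendix C work for a patient who drops ipilimumab and keeps nivolumab, because the last nivolumab dose is then the last study drug. They do not work for the reverse case, which 4.3.2 equally allows.

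Two things are at stake. First, Appendix C is the only place that gives the length of the post-treatment contraception period, and it starts that period at the last nivolumab dose. The longer ipilimumab continues alone, the less of the period remains after the last study drug, until none does. Pregnancy reporting under 7.3 still runs its full length from the last study drug, so the prevention and reporting windows separate. Second, the End of Treatment assessments and the correlative sample can be taken during dosing and labelled as end of treatment. Sites that follow different passages would handle the same patient differently. These patients have already had a toxicity that led to one drug being stopped.

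**Working it through.** The plan states no figure to reproduce. The check is calendar arithmetic on the planned schedule, followed by a comparison of reference dates.

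**Inputs.** Nivolumab every 14 days on Days 1 to 99, then every 28 days from Day 113 (4.2.1 and Table 1). Ipilimumab on Days 1 and 43 of each 84-day cycle, that is every 42 days: Days 1, 43, 85, 127, 169, 211, 253, 295 (Table 1). Assumptions: a month is 30.44 days, so 5 months ≈ 152 days and 7 months ≈ 213 days; ipilimumab continues alone on its planned days.

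**Worked case: last nivolumab on Day 57.**

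- End of Treatment visit: 57 + 30 = Day 87, window Day 80 to 94. Ipilimumab is due on Day 85 and again on Day 127, so the visit falls during dosing.
- Appendix C, FOCBP: 57 + 152 = Day 209. The first ipilimumab dose outside is Day 211. With the −2/+4 day visit window that dose could be given on Day 209, but the following one, Day 253, is well outside.
- Appendix C, males: 57 + 213 = Day 270. The first ipilimumab dose outside is Day 295.

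**Any other last nivolumab day.** The next planned ipilimumab dose after a nivolumab dose is 14, 28 or 42 days later, and further doses follow every 42 days.

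| Next ipilimumab dose | First dose beyond 152 days | First dose beyond 213 days |
|---|---|---|
| +14 | 14 + 4×42 = +182 | 14 + 5×42 = +224 |
| +28 | 28 + 3×42 = +154 | 28 + 5×42 = +238 |
| +42 | 42 + 3×42 = +168 | 42 + 5×42 = +252 |

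Day 57 is the +28 row. Three or four ipilimumab doses fall inside the 5-month window and five inside the 7-month window, so the mismatch needs several further doses on ipilimumab alone before the window is used up.

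**Post-treatment period left after the last ipilimumab dose (FOCBP, last nivolumab Day 57).**

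- Last ipilimumab Day 127: Appendix C leaves 209 − 127 = 82 days. Reporting under 7.3 runs to 127 + 152 = Day 279, so 279 − 209 = 70 days have reporting without a contraception period.
- Last ipilimumab Day 211: Appendix C leaves nothing. Reporting under 7.3 runs to 211 + 152 = Day 363.

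The shortfall equals the time from the last nivolumab dose to the last ipilimumab dose, up to the whole window.

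**Adverse event recording.** The passages that govern recording use wider reference dates. The next sentence of footnote 17 reads "Adverse events will be recorded for up to 30 days after stopping treatment (SAE's for 100 days". Section 2.2.3, the secondary safety objective, runs to 30 days after study treatment. Section 7.2.3 runs to 100 days after the last study drug. Section 8.2.11 runs to 30 days after the last ipilimumab dose. A patient on ipilimumab alone is still on study treatment under each of these.

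**The case against.** The strongest reply is that the documents taken together protect this patient. Criterion 3.1.10 requires contraception for the whole of treatment. Footnote 17 does not name ipilimumab alone at all, and staff would hardly hold a visit with that title during ongoing dosing. Footnote 12 describes ipilimumab only in combination with nivolumab, and no schedule is given for ipilimumab alone.

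Much of this stands. A reader might infer that contraception simply lapses during dosing. That follows only from Appendix C read alone, since 3.1.10 covers the duration of treatment. A reader might also infer from 8.1.11 and footnote 17 that adverse event recording closes 30 days after nivolumab and that the safety endpoint misses events on ipilimumab. The documents do not support this: 8.1.11 is one half of a pair with 8.2.11, and the recording rules in footnote 17, 2.2.3 and 7.2.3 run from the end of treatment or the last study drug.

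What the reply does not repair is the post-treatment contraception period. Criterion 3.1.10 gives no length for it, and Appendix C gives the length only from nivolumab. Nor does it supply an End of Treatment visit after ipilimumab alone: if footnote 17 is read as not covering that patient, no visit is defined. Footnote 12 does not remove the pathway; it is a further conflict with 4.3.2.

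**Conclusion.** The point holds as an inconsistency of reference dates. With ipilimumab continued more than 5 months (FOCBP) or 7 months (males with FOCBP partners) after the last nivolumab dose, Appendix C leaves no post-treatment contraception period, in conflict with 3.1.10 and out of step with 7.3. Footnote 17 either places the End of Treatment visit and its blood sample 23 to 37 days after the last nivolumab dose while ipilimumab is ongoing, or defines no visit for this patient.

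This rests on 4.3.2 meaning what it says about stopping one drug, on ipilimumab then following its planned days, and on the month length used above. The documents do not say how many patients would stop nivolumab alone. No error rate, power or sample size figure changes, and no under-count of adverse events is shown.

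**What to change.** Reconcile Appendix C with 3.1.10 and 7.3. Reconcile footnote 17, together with footnote 12 and sections 4.8, 8.1.11 and 8.2.11, with 4.3.2. The result should be one consistent reference date that covers a patient left on either drug alone, and a clear statement of when that patient has the End of Treatment visit and the correlative sample. Which date applies and how long each window lasts are for the sponsor to decide.

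The cost is wording in a few places through an amendment. No design element, sample size or analysis changes. Depending on the date chosen, the visit and contraception timing of some patients may change.

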6.0 ENDPOINT ASSESSMENT

6.1 Definitions

For the purposes of this study, patients should be re-evaluated for response every 12 weeks (± 7 days). In addition to a baseline scan, confirmatory scans should also be obtained 8 weeks following initial documentation of objective response greater than Stable Disease (SD). Tumor assessments for all subjects should continue as per protocol even if dosing is interrupted. Tumor measurements should be made by the same investigator or radiologist for each assessment whenever possible.

Response and progression will be evaluated in this study using the new international criteria proposed by the revised Response Evaluation Criteria in Solid Tumors (RECIST) guideline (version 1.1).⁴⁴ Changes in the largest diameter (unidimensional measurement) of the tumor lesions and the shortest diameter in the case of malignant lymph nodes are used in the RECIST criteria.

High resolution CT with oral/intravenous contrast or contrast-enhanced MRI is the preferred imaging modalities for assessing radiographic tumor response. If a subject has a known allergy to contrast material, please use local prophylaxis standards to obtain the assessment with contrast if at all possible, or use the alternate modality. In cases where contrast is strictly contraindicated, a non-contrast scan will suffice. Screening assessments should be performed within 28 days of registration. Brain MRI is the preferred imaging method for evaluating CNS metastasis, and assessment is only required during screening for patients who have a known history of CNS disease. All known or suspected sites of disease (including CNS if history of CNS metastases) should be assessed at screening and at subsequent assessments using the same imaging method and technique. If more than one method is used at screening, then the most accurate method according to RECIST 1.1 should be used when recording data, and should again be used for all subsequent assessments. Previously treated CNS metastases are not considered measurable lesions for purposes of RECIST determined response. Subjects with a history of brain metastasis should have surveillance MRI approximately every 12 weeks, or sooner if clinically indicated.

6.2 Primary Endpoint

Median progression-free survival (PFS) as well as PFS at 6 and 12 months [defined the absence of death and of progression of disease. The Response Evaluation Criteria in Solid Tumors (RECIST 1.1) criteria will be used for objective tumor response assessment].⁴⁴

- Clinical and radiological assessments will be performed every 12 weeks (± 7 days) while on treatment. All patients who receive at least one dose of nivolumab and have had their disease re-evaluated will be included in the primary analysis of PFS.

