2.0 OBJECTIVES & ENDPOINTS

2.1 Primary Objective & Endpoint

To assess median progression-free survival (PFS) as well as PFS at 6 and 12 months in patients with recurrent or metastatic adenoid cystic carcinoma (ACC) treated with a combination of nivolumab and ipilimumab.⁴⁴ Patients will have scans every 12 weeks. Efficacy will be evaluated in all patients who receive at least one dose of study treatment and have had their disease re-evaluated.

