2.2 Secondary Objectives & Endpoints

2.2.1 To assess the efficacy of nivolumab and ipilimumab according to response rate (RR), disease control rate (DCR; CR, PR, and SD at 6 and 12 months), overall survival (OS) and progression free survival (PFS) using RECIST criteria in patients with recurrent or metastatic ACC. ⁴⁴

The time in months from start of treatment to progression or death will be measured for all patients who receive at least one dose of study drug. Patients will be followed up to 2 years after completion of treatment. Efficacy will be evaluated in all patients who receive at least one cycle of study treatment.

2.2.2 To assess the efficacy of nivolumab and ipilimumab according to ORR, DCR, PFS, and OS in patients with recurrent or metastatic ACC using irRECIST criteria.⁴⁵ Efficacy will be evaluated in all patients who receive at least one dose of study treatment and have had their disease re-evaluated.

2.2.3 To assess the safety and tolerability profile of nivolumab and ipilimumab therapy in patients with recurrent or metastatic ACC using CTCAE version 4.03. The number, frequency, and severity of adverse events will be collected from time of consent until 30 days after study treatment for all patients who receive at least one dose of study drug.

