6.3 Secondary Endpoints

- Progression free survival defined as time in months from the date of first study treatment to the date of disease progression or death from any cause, whichever comes first. Overall survival (OS) is defined as time in months from the date of first study treatment to the date of death. All patients who receive at least one dose of nivolumab and have had their disease re-evaluated will be included in the secondary analyses of PFS and OS.
- Clinical Benefit Rate at 6 and 12 months (CBR, defined as CR + PR + Stable Disease (SD)) in patients with advanced progressive adenoid cystic carcinoma treated with nivolumab and ipilimumab using RECIST v1.1.
- To assess the efficacy of the regimen according to ORR, CBR, PFS, and in the above population using immune-related response criteria (irRECIST) criteria.⁴⁵

NU Study Number: NU 16N03
BMS Study Number: CA 209-802

- The number, frequency, and severity of adverse events will be collected from the time of consent until 12 weeks after study treatment to evaluate safety of nivolumab in patients with advanced progressive adenoid cystic carcinoma. Adverse events will follow National Cancer Institute Common Terminology Criteria for Adverse Events (CTCAE) version 4.03
- Overall survival defined as time in months from the date of first study treatment to the date of death.

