10.3 Data Analyses Plans

Response rates and 95% confidence intervals will be calculated using exact binomial probability distributions for discrete outcomes. Progression-free survival and overall survival will be graphically depicted using Kaplan-Meier curves. Adverse events will be summarized descriptively using frequencies and percentages. Statistics will be given on type, severity, frequency and attribution of adverse events. Sample size considerations are described above.

An intention to treat analysis will be done. In a single group Phase II study, intention to treat means that all patients who are evaluated and registered for the study are followed and analyzed regardless of (a) whether they were subsequently found to be protocol ineligible and (b) the amount of study treatment (nivolumab/ipilimumab) they received. To calculate progression-free and overall survival in patients who received nivolumab/ipilimumab, times will be taken from the time of study registration. This definition parallels the definition of intention to treat in randomized clinical trials.

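### The plan names conflicting analysis sets for primary PFS and for OS; under 6.2 and 6.3 a treated patient who dies before any re-evaluation drops out of both

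*Combined protocol and SAP*

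**What the plan says.** The combined protocol and SAP describes the efficacy population in several ways.

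- **2.1 (primary objective):** "Efficacy will be evaluated in all patients who receive at least one dose of study treatment and have had their disease re-evaluated". Section 2.2.2 repeats this condition for the irRECIST analyses.
- **6.2 (primary endpoint):** patients with at least one nivolumab dose who "have had their disease re-evaluated will be included in the primary analysis of PFS".
- **6.3 (secondary endpoints):** patients with at least one nivolumab dose who "have had their disease re-evaluated will be included in the secondary analyses of PFS and OS". The same section defines PFS as "time in months from the date of first study treatment to the date of disease progression or death from any cause".
- **2.2.1:** time to progression or death "will be measured for all patients who receive at least one dose of study drug", but a few lines later "Efficacy will be evaluated in all patients who receive at least one cycle of study treatment". A cycle is 12 weeks.
- **6.8:** at least one nivolumab dose and a radiologic evaluation.
- **10.3:** under intention to treat, "all patients who are evaluated and registered for the study are followed and analyzed regardless of" later ineligibility or the amount of treatment received. The next sentence, on calculating PFS and OS, refers to patients who received nivolumab/ipilimumab and says "times will be taken from the time of study registration".

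No section ranks these statements. Re-evaluated is not defined: 6.2 and footnote 3 of 5.0 mention clinical as well as radiological assessment, and the mandatory baseline scan would literally satisfy 6.8.

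**The concern.** PFS counts death from any cause and OS counts only death, so neither endpoint needs a scan for a death to be known. The first scheduled re-evaluation is at week 12. A treated patient who dies earlier without one has both events under the 6.3 definitions, yet 6.2 and 6.3 remove that patient. What remains is a curve conditional on reaching a re-evaluation. This is a single-arm trial, so no comparator shares the distortion.

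Two analysts could each follow the written plan and report different primary PFS and OS from the same data, and the set could be chosen after the data are seen.

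**Working it through.** **1. The plan's own design figures.** Inputs from 10.2: null 0.45, alternative 0.65, 15 patients in stage 1, 43 in total, rejection at 24 or fewer. Take a stage-1 stop at 7 or fewer successes. With X1 the stage-1 successes:

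- Early termination = P(X1 ≤ 7 | 15, 0.45) = 0.6535 (stated 0.654).
- Expected N = 15 + (1 − 0.6535) × 28 = 24.70 (stated 24.70).
- Type I error = Σ over x = 8..15 of P(X1 = x) × P(Bin(28, 0.45) ≥ 25 − x) = 0.0481 (stated 0.048).
- Power, same sum at 0.65 = 0.8035, so type II error 0.196 (stated 0.196).

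The figures reproduce with that stop. The written rule, 7 or more of 15 withdrawn, is a stop at 8 or fewer successes and gives type I error 0.037 and power 0.704. That is a separate matter, but every error rate below carries the condition.

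**2. Effect on a PFS rate.** Let f be the fraction who die before any re-evaluation. With no other censoring, at any time after those deaths, S(re-evaluated) = S(all treated)/(1 − f). The documents give no f, and 10.2 does not define P; reading P as 6-month PFS is an assumption.

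| Assumed f | True 45% reads |
|---|---|
| 5% | 0.45/0.95 = 47.4% |
| 10% | 0.45/0.90 = 50.0% |
| 15% | 0.45/0.85 = 52.9% |

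Per patient, 0.45 × 43 = 19.35. Excluding 1, 2, 3 or 4 early deaths gives 19.35/42, /41, /40 and /39 = 46.1%, 47.2%, 48.4% and 49.6%. The factor 1/(1 − f) applies to OS as well.

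**3. Effect on the median.** Progression is seen mainly at 12-week scans, so the median moves in steps. Let K ~ Bin(43, f) be the early deaths and, given K, let X ~ Bin(43 − K, s/(1 − f)) be the patients progression-free just after the week-24 scan, where s is the true rate in all treated patients. The median moves from week 24 or earlier to a later scan when X/43 ≤ 0.5 but X/(43 − K) > 0.5. Exact probabilities:

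| s | f = 5% | f = 10% | f = 15% |
|---|---|---|---|
| 45% | 8.5% | 21.4% | 35.4% |
| 65% | 1.2% | 1.9% | 2.1% |
| 35% | 1.5% | 4.8% | 10.2% |

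Simulation of the same model gives about 8/21/36%, 1/2/2% and 1/4/11%. The shift is appreciable mainly when the median sits near the week-24 scan.

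**4. Excluded patients who are alive.** A patient who stops before week 12 without a scan can remain in survival follow-up for 2 years (4.8, 4.9). Illustration with assumed numbers: 20 of 43 alive is 46.5%; excluding 3 unscanned survivors leaves 17/40 = 42.5%. OS then reads lower.

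**5. The go/no-go count.** If the 15 and the 43 are treated patients and early deaths are non-successes, f does not enter and the error rates in step 1 stand. If both stages were filled with re-evaluated patients only, the success rate among them would be 0.45/(1 − f). With a stop at 7 or fewer, type I error would be 0.087, 0.153 and 0.258 at f = 5, 10 and 15%.

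**6. Time origin.** It is first treatment in 6.3 and registration in 10.3. Footnote 15 of 5.0 starts treatment within 7 days of registration, so the gap is at most 7 days.

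**The case against.** The best defence is that 10.3 is the statistics section, orders intention to treat, and so overrides loose wording elsewhere. But 6.2 is the more specific text and names the primary analysis, and 10.3 is itself divided between all registered patients and patients who received the drugs. Nor does the word evaluated in 10.3 rescue the reading: it precedes registered, and 3.0 uses it for eligibility. The defence does show that 10.3 cannot be cited as a clean all-registered rule for PFS and OS.

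A second defence is that the effect is small. One to four early deaths move 45% by 1.1 to 4.6 points, while an exact 95% interval at 19/43 runs from about 29% to 60%. Footnote 4 of 5.0 allows earlier scans, which would reduce f. This stands, and it limits the severity.

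A reader might infer two stronger claims. One is that the restriction can only make PFS and OS read high. That holds for excluded early deaths, but step 4 shows that excluded survivors can pull OS down. The other is that the go/no-go test is inflated. Section 4.5 speaks of up to 43 treated subjects and 4.10 replaces only untreated patients, so the documents do not establish it. The opposite assurance is not secure either: 4.5 bases stage 1 on the first 15 evaluable patients, and 6.4 and 6.8 tie evaluability for response or efficacy to re-evaluation or radiology.

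**Conclusion.** The contradiction is real and unresolved in the documents. If 6.2 and 6.3 are followed, deaths before any re-evaluation leave analyses in which they are events by definition, and this biases PFS and OS upward. The net direction for OS is open once living, unscanned patients are also excluded.

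The size rests on an assumed early-death fraction. A few excluded patients shift a 45% rate by a few points, and the median usually stays where it is. The decision rule is unaffected if both stages count treated patients, and exposed if they are filled with re-evaluated patients only. This should be fixed: it concerns the primary endpoint and the remedy is cheap, but it does not by itself invalidate the design.

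**What to change.** - Delete the re-evaluation condition for PFS and OS in 2.1, 2.2.2, 6.2, 6.3 and 6.8, and the one-cycle condition in 2.2.1.
- Name one primary set: all ACC patients who receive at least one dose, timed from first dose. This fits 6.3's time origin, 4.5, 4.10 and the treated-patient wording in 10.3. Amend the rest of 10.3 to match. An all-registered set would fit poorly: the cut-off is built on 43, 4.10 allows untreated patients to be replaced, and survival follow-up in 4.8 runs from treatment discontinuation.
- PFS: death before any assessment is an event at the date of death. OS: every treated patient is included, censored at the last date known alive.
- In the 24-week count and the response and disease control rates, keep patients with no post-baseline assessment in the denominator as non-successes. Align 6.4 with this.
- In 4.5 replace evaluable with treated, and say in 10.2 that the 43 are treated patients.
- Report the re-evaluated set only as a sensitivity analysis.
- Footnote 3 of 5.0 ends tumor assessment at treatment discontinuation, while 4.8 continues imaging after a stop for toxicity. These must be reconciled.

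The cost of the analysis-set change is wording, with no added patients; survival of treated patients is already followed under 4.8. PFS, OS and rate estimates may come out slightly lower, and the all-registered wording in 10.3 is given up.
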